# 7.7.4 Multiple Comparisons/Multiplicity

The overall hypothesis of no differences between treatment groups is only to be rejected if both treatment comparisons – based on the co-primary efficacy variables – yield a significant result, i.e. if for both tests the hypothesis of no difference between treatment groups can be rejected. Thus, no issue with respect to multiplicity arises and no  $\alpha$ -adjustment is necessary.

Results of all other tests or confidence intervals are only descriptive; a confirmatory interpretation is not valid in this context.

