#### Duration of treatment and assessment

The length of each injection cycle was chosen on the basis of reported observations that the effect of *Botulinum* toxin builds up over approximately two weeks after treatment and decays after 8–12 weeks [Chinnapongse 2012, ClinicalTrials.gov 2011]. Therefore, in order to avoid any unwanted reinforcement of consecutive doses, a separation of 16 weeks (at least 14 weeks) between doses was incorporated into the design.

Sialorrhea manifesting itself as a consequence of neurological disease is a chronic health problem and requires long-term treatment. Therefore, the extension period of this study investigates the efficacy and safety of repeated administration of NT 201, given at fixed intervals. Following the placebo-controlled main period of  $16\pm 2$  weeks' duration, all subjects complying with the eligibility criteria will receive active treatment in the extension period. Each subject will receive at least three injections with NT 201 within an overall treatment period of 64 weeks.

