# 6.1.2 Secondary efficacy variables

[figure not shown]
The following secondary efficacy variables will be analyzed for the subjects aged 6–17 years:

[figure not shown]
- Change in mean uSFR from baseline (V2) to V4 and V5 (Week 8 and 12, respectively).
- GICS at V4 and V5 (Week 8 and 12, respectively).

Page 14 of 46

CONFIDENTIAL Template: tem-sap-v4.0-20151126 File name: MRZ60201\_3091\_1-sap-final v1.0-2019-06-21.docx Page 16 of 46

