# 7.1.1 Primary/Co-primary Efficacy Variable

The main co-primary estimands will be defined as follows:

Objective	Evaluate whether treatment with NT 201 is superior to treatment with placebo with respect to reducing sialorrhea
Population	Subjects treated
Variable(s)	uSFR and GICS, evaluated at 4 weeks after treatment in comparison to baseline
Handling of intercurrent events	To be defined during the BDRM
Population-level summary of the variable(s)	Difference in mean uSFR change from baseline to week 4 / mean GICS at week 4 between NT 201 and placebo

The main analytic approach or primary confirmatory analysis of the co-primary estimands will be a mixed model repeated measurement analysis (MMRM, 2-sided, significance level alpha=0.05) with comparison of least square means between NT 201 and placebo performed on the group of subjects within the FAS aged 6-17 years.

The dependent variables will be the change in uSFR from baseline (V2) to V3 (Week 4) ( $\Delta$ uSFR) and the carer's/parent's GICS at V3 (Week 4), respectively.

The independent variables are defined as treatment group, pooled investigation sites (see section 7.7.6) and age groups (6-9 years, 10-12 years and 13-17 years) as fixed factors, visit\*treatment as interaction term, and visit as repeated factor. To adjust for the baseline status, the MMRM of the uSFR change additionally includes the baseline score of the uSFR as covariate. Since no baseline assessment of the GICS is available, the baseline mTDS rated by the parent(s)/carer is used as covariate in the MMRM model for the GICS.

The following SAS code will be used:

```
proc mixed data = dataset;
  class treatment pooled_site age_group subject visit;
  model AuSFR (GICS) = treatment pooled_site age_group uSFR_baseline
        (mTDS) visit visit*treatment /solution ddfm=kr;
  repeated visit / subject = subject type = un grp = treatment
  LSMeans visit*treatment pooled_site age_group / pdiff CL alpha =
0.05;
run;
```

where:	treatment	= treatment group (NT 201 (6-17 years) and Placebo (6-17 years))
	pooled_site	= pooled investigation sites
	age_group	= age group (6-9 years, 10-12 years and 13-17 years)
	uSFR_baseline	= Value of uSFR at Visit 2 (Baseline)
	mTDS	= Value of mTDS at Visit 2 (Baseline)

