Only if both co-primary efficacy variables show a statistically significant difference compared to placebo the superiority of NT 201 over placebo will be considered to be proven. Therefore, no  $\alpha$ -adjustment for multiple testing is necessary.

Intercurrent events with potential bias on the co-primary endpoints will be identified prior to or during the BDRM. In case these events are judged as relevantly biasing the co-primary endpoints, conservative sensitivity analyses on the MMRM model will be specified during the BDRM.

In addition to the MMRM, an analysis of covariance (ANCOVA) model will be performed on the FAS (age 6-17 years) using observed cases as well as using the baseline observation carried forward approach (BOCF, no effect) for uSFR and imputing missing GICS entries as "no change". The ANCOVA models will be performed by use of the following SAS code:

```
proc mixed data = dataset;
  class treatment pooled_site age_group;
  model AuSFR (GICS) = treatment pooled_site age_group uSFR_baseline
        (mTDS)/solution ddfm=kr;
  LSMeans treatment pooled_site age_group / pdiff CL alpha = 0.05;
  where visit = V3;
run;
```

Furthermore, a non-parametric Wilcoxon rank-sum test will be performed as sensitivity analysis of the co-primary efficacy variables to investigate the impact of potential deviations from the assumption of normal distribution. The test will be performed for FAS (age 6-17 years) using observed cases as well as using BOCF for uSFR and "no change" for GICS. The Wilcoxon rank-sum test will be performed by use of the following SAS code:

```
proc npar1way data=dataset wilcoxon;
  class treatment;
  var ΔuSFR;
run;
```

For the GICS, a logistic regression will be performed as sensitivity analysis to the distribution assumption. The responder rate will be determined, i.e. all subjects with GICS entry of at least +1 (Minimally improved).

Treatment arm comparisons with respect to responders based on the GICS entries will be performed analogously to the primary efficacy analysis, but based on estimates of logistic regression models. The dependent variable of these models will be the response to treatment. Treatment group, pooled investigation site and age group will be included as factors into the models. Baseline adjustment will be done by including the baseline values of the mTDS as covariate. The following SAS code will be used for estimation:

```
proc logistic data=dataset desc order=formatted;

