#### 7.1.2 Secondary Efficacy Variables

The analyses of the secondary efficacy variables are also based on the subjects aged within the FAS 6–17 years.

The changes in uSFR from baseline (V2) to V4 and V5 (Week 8 and 12, respectively) and the GICS at V4 and V5 (Week 8 and 12, respectively) are analyzed analogously to the primary efficacy variables by means of a MMRM, ANCOVA and Wilcoxon rank-sum test with the analysis sets and methods to handle missing values as described in Section 7.1.1. Furthermore, the logistic regression will be performed for the GICS at V4 and V5.

Although these are "other" and not "secondary" efficacy variables, the uSFR change from baseline to V6 (Week 16) and the GICS at V6 will be included in the MMRM, ANCOVA and Wilcoxon rank-sum tables to give a complete picture over the main period. Furthermore, the logistic regression will be performed for the GICS at V6.

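### A fixed test sequence at Weeks 8 and 12 would give the secondary efficacy results confirmatory status at no cost to the co-primaries; the present descriptive rule is valid but forgoes this

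*SAP*

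**What the plan says.** The confirmatory claim is confined to Week 4. SAP 7.1.1 tests the uSFR change and the carer's GICS by MMRM at two-sided 0.05 and concludes superiority "Only if both co-primary efficacy variables show a statistically significant difference compared to placebo". SAP 7.7.4 repeats that both comparisons must "yield a significant result, i.e. if for both tests the hypothesis of no difference between treatment groups can be rejected", notes correctly that no alpha adjustment is then needed, and closes: "Results of all other tests or confidence intervals are only descriptive; a confirmatory interpretation is not valid in this context". Protocol 12.4.7.4 carries the identical sentence.

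The secondary efficacy variables in SAP 6.1.2 and protocol 12.3.1.2 are uSFR change and GICS, each at Weeks 8 and 12. Under SAP 7.1.2 they "are analyzed analogously to the primary efficacy variables by means of a MMRM, ANCOVA and Wilcoxon rank-sum test". The same section adds Week 16 to those tables, although it classes Week 16 as an other variable and not a secondary one. The SAS code in SAP 7.1.1 already requests the visit-by-treatment least-squares means with pairwise differences and confidence limits.

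Neither document sets an order, a gate or an alpha split for the secondary variables, and SAP section 8 (changes in the planned analyses) adds none.

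**The concern.** The four secondary tests are pre-specified, randomised comparisons against placebo, and the extension period has no placebo arm. Controlled evidence on how the effect holds up after Week 4 can therefore come only from this first cycle. Under SAP 7.7.4 no result at Week 8 or Week 12, however strong, can carry a confirmatory statement.

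A gated sequence would remove that limit without taking anything from the Week 4 tests. It has to be written down before unblinding, because an order chosen afterwards has no confirmatory standing. What is at stake is the status of the later results in a study that the protocol describes as pivotal. The estimates will be produced regardless.

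**Working it through.** **Inputs from the documents.** Two-sided alpha 0.05 (SAP 7.1.1); 146 NT 201 and 73 placebo (SAP 4); difference 1.0 point, SD 1.93 points, 95% power (SAP 4.2).

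**Inputs assumed, because the documents give none.** The standardised effect for uSFR equals that for GICS; no drop-out; correlation between visits 0 to 0.7; correlation between the two variables 0 to 0.3; effects at Weeks 8 and 12 as stated below.

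**1. The plan's own figure.** With 2:1 allocation, placebo n = (1 + 1/2) × (1.960 + 1.645)² × 1.93² / 1.0² = 72.6, rounded up to 73. The total is 73 + 146 = 219, as stated. SE = 1.93 × √(1/146 + 1/73) = 0.277, and 1.0/0.277 gives a noncentrality of 3.61. Power per test is 95.1% (normal) or 94.9% (noncentral t). The stated 95% reproduces.

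**2. Family-wise error of the sequence.** The order is Week 4 (both variables), Week 8 (both), Week 12 (both), each test at 0.05, stopping at the first step not met. Take the first step in that order at which at least one null hypothesis is true. Any false claim, at that step or later, requires rejecting that true null at 0.05. The chance of any false claim is therefore at most 0.05, whatever the correlations.

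Simulation of six correlated z statistics (300,000 runs per setting) agrees:
- 0.0496 to 0.0504 in the least favourable cases, where one variable is null at the first false step.
- 0.0025 to 0.0093 when all nulls are true.

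The order is needed. If Weeks 8 and 12 are each tested at 0.05 after a Week 4 success but without an order, and one variable is null at both visits, the error is 0.084 to 0.098. For two independent tests it is 1 − 0.95² = 0.0975.

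**3. Cost to the co-primaries.** The Week 4 step comes first and is tested exactly as now: alpha 0.05, N = 219, power 95% per variable.

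**4. Chance that the later steps succeed (illustration only).** With zero correlation this is a product of per-test powers. At 100%, 80% and 60% of the planned effect those powers are 0.951, 0.824 and 0.583.
- Full persistence: Week 8 is 0.951⁴ = 0.82; Week 12 is 0.951⁶ = 0.74.
- Fading to 80% then 60%: Week 8 is 0.951² × 0.824² = 0.61; Week 12 is 0.951² × 0.824² × 0.583² = 0.21.

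Positive correlation raises these. The range runs from correlations 0/0 to 0.7/0.3 (between visits / between variables):

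| Effect at Week 8, Week 12 | Week 8 step met | Week 12 step met |
|---|---|---|
| 100%, 100% | 82–86% | 74–82% |
| 80%, 60% | 61–68% | 21–36% |

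**The case against.** The strongest reply is that nothing here is wrong. Confining confirmation to two co-primaries is a legitimate and conservative choice, and protocol and SAP agree on it word for word. No objective visible in either document asks for a confirmatory statement on persistence: the study objective is efficacy and safety against placebo, and the main estimand is set at Week 4. All of this stands.

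A reader might infer that the trial throws away its evidence on duration. It does not. SAP 7.1.2 reports the placebo comparison at Weeks 8, 12 and also 16, and SAP 7.1 provides for confidence limits and descriptive p-values where appropriate.

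A reader might also infer that duration is a design premise left untested, since protocol 6.2 says the toxin effect "builds up over approximately two weeks after treatment and decays after 8–12 weeks". That passage uses the decay to justify spacing the doses so that their effects do not reinforce each other. It does not make Weeks 8 and 12 tests of duration.

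The success rates are open to challenge too. An SD in points can describe GICS but not uSFR, which is measured in g/min, and no uSFR effect, correlation or drop-out rate for the efficacy analysis is given. Drop-out, which SAP 4.1 anticipates, would lower the rates. The Week 12 step is weakest in the case where the effect fades.

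Finally, requiring both variables at each step is one valid choice. A full ordering of the four single tests would also control the error, with different chances of success.

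None of this touches the central result: the sequence costs the co-primaries nothing, and a failed later step leaves the Week 4 conclusion intact.

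**Conclusion.** The point holds as a free improvement and not as an error. The descriptive rule is valid. What it forgoes is confirmatory status at Weeks 8 and 12, which a fixed sequence would allow with family-wise error held at 0.05 and no change to co-primary alpha, N or power. That part rests on no assumption about effects or correlations.

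How often the later claims would succeed does rest on assumptions (equal standardised effects, no drop-out, the stated correlations), so the rates should be read only as illustrations. The prospect is good if the effect persists, and modest at Week 12 if it fades. The documents do not support the stronger reading that the plan is defective or loses a claim it set out to make. The weight of the point depends on whether the sponsor wants a confirmatory statement beyond Week 4.

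**What to change.** Before unblinding, amend SAP 7.7.4 to say the following. If both co-primary tests are significant, the secondary variables are tested at two-sided alpha 0.05 in fixed order:

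1. uSFR change and GICS at Week 8, both required.
2. uSFR change and GICS at Week 12, both required.

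Testing stops at the first step not met. The tests are the visit-by-treatment contrasts of the primary MMRM on the FAS aged 6–17 years. All other tests and intervals, including Week 16, remain descriptive.

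List the change in SAP section 8 and state there that it supersedes the matching sentence in protocol 12.4.7.4; otherwise the two documents will conflict. Protocol section 12 allows such changes through an amendment to the protocol or the SAP before database close or unblinding.

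The cost is a short SAP amendment. No new model, data or subjects are needed. The SAP file is already marked as final v1.0, dated 21 June 2019, so the amendment should record that it was made while the study was still blinded.

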# 7.7.5 Examination of Subgroups

All subgroup analyses will be performed on an explorative level.

Tables with descriptive statistics for uSFR, GICS, GICS response and mTDS will be repeated for the following subgroups:

- Age group:
  - o 6-9 years,
  - o 10-12 years
  - o 13-17 years.
- Pooled investigational sites (where pooling will be the same as used for the MMRM and ANCOVA models).
- Etiology (cerebral palsy, traumatic brain injury and other)
- Gender
- Weight group (rounded to one decimal place):
  - ]0, 30 kg[ and  $\ge$  37.5kg (corresponds to a planned NT201 exposure of  $\le$  2U/kg)
  - $\circ$  [30, 37.5kg[ (corresponds to a planned NT 201 exposure of > 2U/kg)
- Baseline disease severity:
  - $\circ$  uSFR at baseline  $\leq$  median of uSFR at baseline
  - uSFR at baseline > median of uSFR at baseline

These analyses will be performed for FAS, PPS and SES OLEX for uSFR and GICS. Tables for mTDS will be created for FAS and SES OLEX. The analysis by age group will be performed for FAS (6-17 years) instead of FAS.

In addition, the following uSFR and GICS MMRM models will be built:

- 1. MMRM model with treatment, pooled site and age group included as (fixed) factors and uSFR at baseline (or mTDS at baseline) included as covariate, visit\*treatment and subgroup\*visit\*treatment as interaction terms and visit as repeated factors. I.e. two different models will be calculated (pooled site as interaction term and age group as interaction term).
- Primary endpoint MMRM model based on subjects with uSFR at baseline ≤ median of uSFR at baseline, only.
- 3. Primary endpoint MMRM model based on subjects with uSFR at baseline > median of uSFR at baseline, only.
- 4. MMRM model with treatment, pooled site, age group, etiology, gender, weight group included as (fixed) factors and uSFR at baseline (or mTDS at baseline) included as covariate, visit\*treatment and subgroup\*visit\*treatment as interaction terms and visit as repeated factors. I.e. five different models will be calculated (pooled site as interaction term, age group as interaction term, etiology as interaction term, gender as interaction term and weight group as interaction term).

For each subgroup level of age group and pooled site, the LS-Mean for difference between NT201 and placebo at week 4 will be selected from Model 1) and presented in a table and forest plot.

For the first (second) subgroup level of baseline disease severity, the LS-Mean for difference between NT201 and placebo at week 4 will be selected from Model 2) (3) and presented in the same table and forest plot as mentioned above.

For each subgroup level of etiology, gender and weight group, the LS-Mean for difference between NT201 and placebo at week 4 will be selected from Model 4) and also presented in the above mentioned table and forest plot.

These analyses will be performed for FAS (6-17 years).

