# 4.2 Efficacy

Subjects in age group 6–17 years

The sample size of 219 subjects is sufficient to provide 95% power to detect a statistically significant difference in means of 1.0 point between active treatment-treated and placebo-treated subjects with a standard deviation of 1.93 points (two-sided t test, significance level  $\alpha = 0.05$ ).

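### Baseline severity is examined only as two separate median-half models, so the SAP gives no estimate or CI of how the NT 201 effect changes with severity; an added continuous-interaction model would supply one cheaply

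*SAP*

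**What the plan says.** SAP 7.7.5 (Examination of Subgroups) defines baseline disease severity as uSFR at or below the median against uSFR above it. Two MMRMs follow for each of uSFR and GICS. Model 2 is "Primary endpoint MMRM model based on subjects with uSFR at baseline ≤ median of uSFR at baseline, only" and Model 3 is "Primary endpoint MMRM model based on subjects with uSFR at baseline > median of uSFR at baseline, only". For the forest plot the SAP states: "For the first (second) subgroup level of baseline disease severity, the LS-Mean for difference between NT201 and placebo at week 4 will be selected from", with the lower half taken from Model 2 and the upper half from Model 3.

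The other factors are handled in models fitted to all children in the FAS aged 6–17. Model 1 takes pooled site and age group in turn as the interacting factor. Model 4 does the same with a larger adjustment set: "pooled site as interaction term, age group as interaction term, etiology as interaction term, gender as interaction term and weight group as interaction term". Baseline severity is in neither list.

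Under SAP 7.1.1, "the MMRM of the uSFR change additionally includes the baseline score of the uSFR as covariate", as a main effect only. The GICS model adjusts for baseline mTDS and contains no uSFR term. In the available text, no model lets the treatment effect vary with continuous baseline uSFR.

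The SAP limits the weight of all this: "All subgroup analyses will be performed on an explorative level". SAP 7.7.4 treats every result outside the co-primary comparison as descriptive.

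**The concern.** The question behind a severity subgroup is whether benefit depends on how severe the drooling was at the start. The answer is a difference between effects, or a slope, with its uncertainty. Models 2 and 3 give two effects in disjoint halves, and the reader is left to compare two intervals by eye. With 219 children at 2:1, each half holds on average about 73 NT 201 and 36 placebo children, so both intervals will be wide.

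There is also a possible loss of precision. Baseline uSFR is a continuous measurement, and all variation within a half is ignored as a source of information on effect modification. If the gradient is smooth, a clinically interesting one could go unnoticed in data that would show it on the full scale. The stake is the reading of an exploratory plot, not the trial's conclusion.

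**Working it through.** **Inputs.** From SAP 4 and 4.2: 146 NT 201 and 73 placebo, SD 1.93 points, difference 1.0 point, two-sided 5%. The documents give no distribution for baseline uSFR and no severity gradient, so both are assumed below.

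**Step 1: the plan's own figure.** SE = 1.93 × √(1/73 + 1/146) = 0.277. Power = Φ(1.0/0.277 − 1.96) = Φ(1.65) = 95.1% (94.9% with the t distribution). This agrees with the statement that "The sample size of 219 subjects is sufficient to provide 95% power to detect a statistically significant difference in means of 1.0 point".

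**Step 2: information kept by a median cut.** For an effect that changes linearly with baseline X, with constant residual variance, the share kept is the squared correlation between X and the indicator X > median.
- Normal X: (0.3989/0.5)² = 2/π = 0.637. So 36.3% is lost, and 219 children carry the interaction information of about 139 (219 × 0.637).
- Uniform X: 0.75 kept, 25% lost.
- Gamma with shape 4, 2 and 1: 40.7%, 44.7% and 52.0% lost.
- Lognormal with log-SD 0.25, 0.5 and 0.75: 39.6%, 48.4% and 60.5% lost (72.8% at an extreme log-SD of 1.0).
- Effect linear in log uSFR, with log uSFR normal: 36.3% again.

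**Step 3: what this means for detecting a gradient.** Let D be the difference in mean effect between the upper and lower halves, with a normal baseline.
- Split: SE(D) = √2 × 1.93 × √(1/73 + 1/36.5) = 0.553.
- Continuous: the slope per SD of baseline has SE 1.93/√(219 × 2/9) = 0.277, and D = 2√(2/π) × slope = 1.596 × slope, so SE(D) = 0.442.
- Check: (0.442/0.553)² = 0.64, as in Step 2.

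Power = Φ(D/SE − 1.96). The simulated figures come from 4,000 trials per setting at a single time point.

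| Assumed D (points) | Continuous, analytic | Split, analytic | Continuous, simulated | Split, simulated |
|---|---|---|---|---|
| 1.0 | 62% | 44% | 60% | 42% |
| 1.25 | 81% | 62% | 79% | 59% |
| 1.5 | 92% | 77% | 92% | 75% |

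With a lognormal baseline (log-SD 0.5) the simulated figures are 68%, 87% and 95% against 42%, 60% and 75%.

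**Step 4: the cut or the separate fitting?** With a normal baseline, eight assumed site pools and a gradient set for nominal 80% power, simulated power was 76.7% continuous, 57.3% with the split in one model and 55.3% with two separate models. For nominal 90% it was 87.1%, 69.5% and 67.1%. Almost all of the loss comes from the cut; separate fitting costs about 1 to 2.5 points more.

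**Step 5: where the ranking changes.**
- True step of 1.25 points at the median, normal baseline: split Φ(1.25/0.553 − 1.96) = 62%; continuous Φ(1.25 × 0.3989/0.277 − 1.96) = 44%. Simulations gave 55–61% against 41–43%, so here the split is better.
- No true interaction, lognormal baseline, residual SD rising with the square root of baseline or with baseline itself: the model-based continuous test falsely rejects in about 13–14% and 28% of trials. Log uSFR reduces this to 7% and 15%. Variances estimated separately by arm, as in the SAP code, do not help. Two separate half-models stay near 5%. A robust variance brings the continuous test to about 6%, but its power advantage then shrinks or disappears.

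**The case against.** The strongest reply is that the plan makes no severity test, so power is measured against a contrast the SAP never promised. That stands: the results are exploratory and descriptive. It does not remove the missing interval. The halves are disjoint, so a reader could combine the two planned estimates into a difference with a standard error, but the SAP does not say this will be reported.

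Separate fits also have a merit. Each half estimates its own variance, which protects against a spread of uSFR change that grows with baseline. That is plausible because flow cannot fall below zero, although the documents give no figure. This stands, and it is why Models 2 and 3 should stay and the added model needs a robust variance.

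The SD of 1.93 is in points, which fits GICS; uSFR is in g/min. The power table therefore applies to uSFR only for gradients expressed in SD units (1.0, 1.25 and 1.5 points are 0.52, 0.65 and 0.78 SD).

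A reader might go further than the documents allow in three ways:
- That Models 2 and 3 are the only planned look at severity. SAP 7.7.5 also plans descriptive tables of uSFR, GICS, GICS response and mTDS by severity half, and SAP 7.1.2 mentions other efficacy variables that are not in the available text.
- That the severity rows alone are adjusted differently from the rest of the plot. They use the primary covariates, as Model 1 does for age and site; it is Model 4 that adds factors.
- That a continuous interaction always holds its 5% error rate. Step 5 shows that it does not without constant variance.

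**Conclusion.** The point holds as a low-cost improvement to an exploratory analysis. What follows from the documents alone is that severity is the one listed subgroup factor with no interaction term, and that no estimate or CI for effect modification by severity is planned.

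The information loss is conditional. It is 36% for a linear gradient and a normal baseline, 25% for a uniform one, about 40–60% for moderately skewed ones, and nil for a step at the median, all with constant residual variance. It would be tempting to state a loss of about a third as a property of the plan, but the documents give neither the shape of baseline uSFR nor that of the gradient. Nor do they support any doubt about the co-primary test or the sample size of 219: both are untouched.

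**What to change.** Add to SAP 7.7.5 one exploratory MMRM per outcome on the FAS (6–17 years):
- Start from the primary model and add continuous baseline uSFR × treatment × visit with all lower-order terms. Use log uSFR if baseline is clearly skewed, decided blind to treatment.
- For GICS, also add the baseline uSFR main effect, since that model adjusts only for mTDS.
- Use an empirical (robust) variance with a small-sample correction, and name the degrees-of-freedom method that goes with it, because the Kenward–Roger option in the primary code corrects the model-based variance.
- Report the Week 4 interaction with its 95% CI, and the NT 201 minus placebo difference at the 25th, 50th and 75th percentiles of baseline uSFR in the forest plot.

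Keep Models 2 and 3 and the median-split tables beside it. If the two views disagree, linearity is in doubt and the reader can see it.

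The cost is one extra model per outcome, a few lines of code and SAP text, and a linearity assumption. No new data are needed.
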